8. STUDY PROCEDURES

8.1 Schedule of study procedures

Before study entry, throughout the study, and following study drug discontinuation, various clinical and diagnostic laboratory evaluations are outlined. The purpose of obtaining these detailed measurements is to ensure adequate safety and tolerability assessments. Clinical evaluations and laboratory studies may be repeated more frequently if clinically indicated.

8.1.1 Screening Phase

Screening procedures will be performed up to 28 days before Day 1, unless otherwise specified. All subjects must first read, understand, and sign the IRB -approved ICF before any study-specific screening procedures are performed. After signing the ICF, completing all screening procedures, and being deemed eligible for entry, subjects will be enrolled in the study. Procedures that are performed prior to the signing of the ICF and are considered standard of care may be used as screening assessments if they fall within the 28-day screening window. Refer to the Study Calendar for complete list of all the procedures that will be performed during the Screening Visit.

8.1.2 Treatment Phase

Procedures to be conducted during the treatment phase of the study are presented in the Schedule of Assessments. Screening procedures performed within 7 days of Cycle 1 Day 1 (C1D1) do not need to be repeated on C1D1.

8.1.3 End of Treatment

End of treatment is defined as the last planned dose of tremelimumab and durvalumab. This will be followed by physician's choice of systemic therapy, followed by standard of care surgical intervention. Any further adjuvant therapy is at the discretion of the treating physician. Also, should the treating physician deem it is in the patient's best interest to proceed with surgery after the completion of the 2 doses each of tremelimumab and durvalumab, the physician may proceed with surgery with adjuvant therapies as per physician discretion.

All subjects will be followed until the time of breast surgery.

8.2 Description of study procedures

8.2.1 Medical history and physical examination, electrocardiogram, weight and vital signs

Findings from medical history (obtained at screening) and physical examination shall be given a baseline grade according to the procedure for AEs. Increases in severity of pre-existing conditions during the study will be considered AEs, with resolution occurring when the grade returns to the pre-study grade or below.

Physical examinations will be performed on study days noted in the Schedule of Assessments.

8.2.2 Physical examination

Physical examinations will be performed according to the assessment schedule. Full physical examinations will include assessments of the head, eyes, ears, nose, and throat and the respiratory, cardiovascular, GI, urogenital, musculoskeletal, neurological, dermatological, hematologic/lymphatic, and endocrine systems. Height will be measured at Screening only. Targeted physical examinations are to be utilized by the Investigator on the basis of clinical observations and symptomatology. Situations in which physical examination results should be reported as AEs are described in Section 10.

8.2.3 Electrocardiograms

Resting 12-lead ECGs will be recorded at screening and as clinically indicated throughout the study. ECGs should be obtained after the patient has been in a supine position for 5 minutes and recorded while the patient remains in that position.

At Screening, a single ECG will be obtained on which QTcF must be <470 ms. If an ECG is interpreted to be a prolonged QT interval, 2 additional ECGs will be obtained and the PI will then evaluate all 3 ECGs to determine whether the patient should be excluded.

In case of clinically significant ECG abnormalities, including a QTcF value >470 ms, 2 additional 12-lead ECGs should be obtained over a brief period (eg, 30 minutes) to confirm the finding.

Situations in which ECG results should be reported as AEs are described in Section 10.0.

8.2.4 Vital signs

Vital signs (blood pressure [BP], pulse, temperature, and respiration rate) will be evaluated according to the assessment schedules.

On infusion days, patients will be monitored during and after infusion of durvalumab + tremelimumab as presented in the bulleted list below.

BP will be measured using a semi-automatic BP recording device with an appropriate cuff size, after the patient has rested for at least 5 minutes. BP and pulse will be collected from patients receiving durvalumab + tremelimumab treatment before, during, and after each infusion at the following times (based on a 60-minute infusion):

Prior to the beginning of the infusion (measured once from approximately 30 minutes before up to 0 minutes [ie, the beginning of the infusion]).

Halfway through the infusion (approximately 30 minutes \pm 10 minutes).

At the end of the infusion (approximately 60 minutes \pm 10 minutes), 30 minutes, and 60 minutes after the infusion (i.e. 90 and 120 minutes from the start of the infusion) (\pm 10 minutes) – for the first infusion only and then for subsequent infusions as clinically indicated.

A 1-hour observation period is required after the first infusion of durvalumab and tremelimumab. If no clinically significant infusion reactions are observed during or after the first cycle, subsequent infusion observation periods can be at the Investigator's discretion (suggested 30 minutes after each durvalumab and tremelimumab infusion).

If the infusion takes longer than 60 minutes, then BP and pulse measurements should follow the principles as described above or be taken more frequently if clinically indicated. The date and time of collection and measurement will be recorded on the appropriate electronic medical record. Additional monitoring with assessment of vital signs is at the discretion of the Investigator per standard clinical practice or as clinically indicated.

Situations in which vital signs results should be reported as AEs are described in Section 10.3. A complete physical examination will be performed and will include an assessment of the following (as clinically indicated): general appearance, respiratory, cardiovascular, abdomen, skin, head and neck (including ears, eyes, nose and throat), lymph nodes, thyroid, musculo-skeletal (including spine and extremities), genital/rectal, and neurological systems and at screening only, height.

8.2.5 Clinical laboratory tests

The following clinical laboratory tests will be performed (see the Schedule of Assessments):

- Coagulation parameters: Activated partial thromboplastin time and International normalized ratio to be assessed at baseline and as clinically indicated
- Pregnancy test (female subjects of childbearing potential only)
 - Urine human chorionic gonadotropin
- Thyroid Stimulating Hormone
 - free T3 and free T4 only if TSH is abnormal
- Other laboratory tests
 - Hepatitis A antibody, hepatitis B surface antigen, hepatitis C antibody
 - HIV antibody for patients with known history

Table 5. Hematology Laboratory Tests

Basophils	Mean corpuscular volume
Eosinophils	Monocytes
Hematocrit	Neutrophils
Hemoglobin	Platelet count
Lymphocytes	Red blood cell count
Mean corpuscular hemoglobin	Total white cell count
Mean corpuscular haemoglobin concentration	

Table 6. Clinical chemistry (Serum or Plasma) Laboratory Tests

Albumin	Glucose
Alkaline phosphatase	Lactate dehydrogenase
Alanine aminotransferase	Lipase
Amylase	Magnesium
Aspartate aminotransferase	Potassium
Bicarbonate	Sodium
Calcium	Total bilirubin ^a
Chloride	Total protein
Creatinine	Urea or blood urea nitrogen, depending on local practice
Gamma glutamyltransferase ^b	Uric acid

^a If Total bilirubin is $\geq 2 \times \text{ULN}$ (and no evidence of Gilbert's syndrome) then fractionate into direct and indirect bilirubin

^b At Screening, Day 1, and as clinically indicated.

Table 7. Urinalysis Tests^a

Bilirubin	pH
Blood	Protein
Glucose	Specific gravity
Ketones	Colour and appearance

^a Microscopy should be used as appropriate to investigate white blood cells and use the high power field for red blood cells

8.3 Biospecimen collections

Blood and tissue specimens will be collected as specified in the Schedule of Study Assessments. Specimens will be de-identified and labelled with a unique study identification number for use in immune monitoring assays. Assays will be performed in research laboratories at the University of Texas MD Anderson Cancer Center to include the Immunotherapy Platform.

8.3.1 Tumor biopsies and surgical specimen

All patients will have biopsies performed before starting treatment with tremelimumab + durvalumab and post-treatment with tremelimumab + durvalumab (before starting neoadjuvant chemotherapy). These biopsies will be obtained by core needle using a needle gauge of 14 or larger, with up to five cores obtained at each time point. Surgical resection specimens will be obtained with the amount of tissue provided determined by the attending breast pathologist performing the gross sectioning at the time of surgical resection.

All samples will be collected and analyzed as per a separate IRB-approved lab protocol (PA13-0291). The Immunotherapy Platform will perform immune monitoring, including but not limited to evaluation of CD4 and CD8 T cells in available tumor samples as previously published (Liakou et al 2008; Carthon et al 2010; Tang et al 2013; Chen et al 2014; Eng et al 2015; Chen et al 2016; Subudhi et al 2016; Gao et al 2016).

8.3.2 Peripheral blood and serum samples

Multiple blood draws will be required for this trial (pre-treatment, post-treatment, at time of surgery). All blood collections will be compliant with the institutional safety standards and will not exceed the maximum blood draw per venipuncture policy. All samples will be collected and analyzed as per a separate IRB-approved lab protocol (PA13-0291). The Immunotherapy Platform will perform immune monitoring, including but not limited to evaluation of CD4 and CD8 T cells in available blood samples as previously published (Liakou et al 2008; Carthon et al 2010; Tang et al 2013; Chen et al 2014; Eng et al 2015; Chen et al 2016; Subudhi et al 2016; Gao et al 2016).

9. DISEASE EVALUATION AND METHODS

As this is a pre-surgical pilot study, evaluations will be done primarily by mammogram and breast ultrasound at baseline and then by ultrasound at the completion of the 2 cycles of investigational therapy.

At the time of surgery the residual tissue will be described by Residual Cancer Burden (RCB) (Symmans et al 2007). The RCB is a continuous variable derived from the primary tumor dimensions, cellularity of the tumor bed, and axillary nodal burden. RCB can be divided into four classes (RCB-0 to RCB-III) and will be collected as part of the study.

RCB-0 (pCR), Minimal RCB (RCB-I), Moderate RCB (RCB-II), and Extensive RCB (RCB-III)

The following parameters are required from pathologic examination in order to calculate

Residual Cancer Burden (RCB) after neoadjuvant treatment:

1. The largest two dimensions (mms) of the residual tumor bed in the breast (largest tumor bed if multicentric disease)
2. Submission of the entire largest cross-sectional area of the residual tumor bed for histologic mapping, with specific identification of those slides in the pathology report (e.g. "the largest cross-sectional area of primary tumor bed was submitted in cassettes A5 - A9")
 - If the residual tumor is large (i.e. largest diameter > 5 cm), then at least 5 representative cassettes from the largest cross-sectional area are sufficient, but should be identified in the original pathology report (e.g. "representative sections from the largest cross-sectional area of primary tumor bed were submitted in cassettes A5 - A9")
3. Histologic assessment of the percentage of the tumor bed area that contains carcinoma (all carcinoma, i.e. invasive and in situ), select one of the following:
0%, 1%, 5%, 10%, 20%, 30%, 40%, 50%, 60%, 70%, 80%, 90%
 - To assess cellularity it is helpful to scan across the sections of tumor bed and then estimate the average cellularity from the different microscopic fields.
 - When estimating percentage cancer cellularity in any microscopic field, compare the involved area with obvious standards, e.g. more or less than half, one quarter, one fifth, one tenth, one twentieth, etc.
 - Expect there to be variable cellularity within the cross section of any tumor bed, but estimate the overall cellularity from the average of the estimates in different microscopic fields of the tumor bed.
 - e.g. if cellularity in different fields of the tumor bed were estimated as 20%, 10%, 20%, 0%, 20%, 30%, then an average estimate of overall cellularity would be 20%.
4. Histologic estimate of the percentage of the carcinoma in the tumor bed that is in situ, select one of the following:
0%, 1%, 5%, 10%, 20%, 30%, 40%, 50%, 60%, 70%, 80%, 90%, 100%
5. The number of positive (metastatic) lymph nodes
6. The largest diameter (mm) of the largest nodal metastasis

The RCB can be accessed online: www.mdanderson.org/breastcancer_RCB. The RCB will be determined using this online calculator and documented by the study staff in the patient's electronic medical record as part of the off study note.

10. ASSESSMENT OF SAFETY

The Principal Investigator is responsible for ensuring that all staff involved in the study is familiar with the content of this section.

10.1 Safety Parameters

10.1.1 Definition of adverse events

The International Conference on Harmonization (ICH) Guideline for Good Clinical Practice (GCP) E6 (R1) defines an AE as:

Any untoward medical occurrence in a patient or clinical investigation subject administered a pharmaceutical product and which does not necessarily have a causal relationship with this treatment. An AE can therefore be any unfavorable and unintended sign (including an abnormal laboratory finding), symptom, or disease temporally associated with the use of a medicinal product, whether or not considered related to the medicinal product.

An AE includes but is not limited to any clinically significant worsening of a subject's pre-existing condition. An abnormal laboratory finding (including ECG finding) that requires an action or intervention by the investigator, or a finding judged by the investigator to represent a change beyond the range of normal physiologic fluctuation, should be reported as an AE.

Adverse events may be treatment emergent (ie, occurring after initial receipt of investigational product) or nontreatment emergent. A nontreatment-emergent AE is any new sign or symptom, disease, or other untoward medical event that begins after written informed consent has been obtained but before the subject has received investigational product. Only AEs related to study drug (durvalumab + tremelimumab) will be followed. Non-treatment-emergent AEs will not be followed. In addition, AEs attributable to the preplanned neoadjuvant chemotherapy or surgery will not be collected.

The term AE is used to include both serious and non-serious AEs.

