Durvalumab, 1500 mg Q4W (equivalent to 20 mg/kg Q4W) for 2 doses/cycles in patients ≥ 30 kg
Tremelimumab 75 mg Q4W (equivalent to 1 mg/kg Q4W) for 2 doses/cycles in patients ≥ 30 kg
Weight-based dosing should be utilized for patients <30 kg durvalumab 20 mg/kg Q4 and tremelimumab 1 mg/kg Q4

Study Assessments and Criteria for Evaluation:

The study's primary endpoints are to evaluate the feasibility of enrolling patients with HR+/HER2- breast cancer onto a trial evaluating investigational agents prior to initiating standard neoadjuvant chemotherapy and to evaluate the safety and tolerability of tremelimumab plus durvalumab in patients with HR+/HER2- breast cancer.

Feasibility Assessments:

Feasibility will be measured by 2 achievements. If both are met, then upfront treatment with tremelimumab plus durvalumab will be feasible for future trials in HR+/HER2- breast cancer patients. The 2 measures are:

- Patients are willing to enroll. This will be established if we can enroll all 15 patients within 12 months of starting the study.
- Patients can complete the protocol. If at least 10 patients complete the study and have available immune data, the trial meets this feasibility criterion.

Safety Assessments:

All patients who receive at least one dose of study drug will be included in the safety monitoring and safety analysis. For trial monitoring and decisions about future trials, a patient will be determined to have an extreme toxicity (ETOX) if either condition is met:

- The patient experiences any grade 3 or higher adverse event (AE) that is possibly, probably, or definitely related to therapy received on this protocol and occurs up to 90 days after the last dose of therapy (durvalumab + tremelimumab). As an exception, any such AE that is potentially treatable with steroids will only count as an ETOX if it does not improve to grade 1 or better within 2 weeks.
- The patient has a delay in surgery of 6 weeks or more due to AE, even if that AE does not meet the definition of ETOX

Statistical Methods and Data Analysis:

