10.1.2 Definition of serious adverse events

A serious adverse event is an AE occurring during any study phase (i.e., screening, run-in, treatment, wash-out, follow-up), at any dose of the study drugs that fulfils one or more of the following criteria:

Results in death

Is immediately life-threatening

Requires in-patient hospitalization or prolongation of existing hospitalization

Results in persistent or significant disability or incapacity

Is a congenital abnormality or birth defect in offspring of the subject

Is an important medical event that may jeopardize the patient or may require medical intervention to prevent one of the outcomes listed above:

- Medical or scientific judgment should be exercised in deciding whether expedited reporting is appropriate in this situation. Examples of medically important events are intensive treatment in an emergency room or at home for allergic bronchospasm, blood dyscrasias, or convulsions that do not result in hospitalizations; or development of drug dependency or drug abuse (21 CFR 312.32).

Important medical events, as defined above, also may be considered SAEs. Any important medical event can and will be reported as an SAE if deemed appropriate by the Principal Investigator or The University of Texas MD Anderson Cancer Center's IND Office.

All events occurring during the conduct of a protocol and meeting the definition of a SAE must be reported to the IRB in accordance with the timeframes and procedures outlines in the "The University of Texas MD Anderson Cancer Center Institutional Review Board Policy for Investigators on Reporting Serious Unanticipated Adverse Events for Drugs and Devices". Unless stated otherwise in the protocol, all SAEs, expected or unexpected, must be reported to the IND Office, regardless of attribution (within 5 working days of knowledge or the event).

All life-threatening or fatal events, that are unexpected, and related to the study drug, must have a written report submitted within 24 hours (next working day) of knowledge of the event to the Safety Project Manager in the IND Office.

Unless otherwise noted, the electronic SAE application (eSAE) will be utilized for safety reporting to the IND Office and The University of Texas MD Anderson Cancer Center IRB.

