10.3.1 Study recording period and follow-up for adverse events and serious adverse events

Adverse events and serious adverse events will be recorded from time of first protocol intervention, throughout the treatment period and including the follow-up period (90 +/-7 days after the last dose of durvalumab + tremelimumab).

During the course of the study all AEs and SAEs should be proactively followed up for each subject. Every effort should be made to obtain a resolution for all events, even if the events continue after discontinuation/study completion.

If a subject discontinues from treatment for reasons other than disease progression, and therefore continues to have tumor assessments, drug or procedure-related SAEs must be captured until the patient is considered to have confirmed PD and will have no further tumor assessments.

The investigator is responsible for following all SAEs until resolution, until the subject returns to baseline status, or until the condition has stabilized with the expectation that it will remain chronic, even if this extends beyond study participation.

Follow-up of unresolved adverse events

Any AEs that are unresolved at the subject's last visit (90 days post End of Treatment) in the study are followed up by the investigator for as long as medically indicated, but without further recording. After 90 days, only subjects with ongoing investigational product-related SAEs will continue to be followed for safety.

AstraZeneca/MedImmune and the IND Office retain the right to request additional information for any subject with ongoing AE(s)/SAE(s) at the end of the study, if judged necessary.

Post study events

After the subject has been permanently withdrawn from the study, there is no obligation for the investigator to actively report information on new AE or SAEs occurring in former study subjects after the 90-day safety follow-up period for patients treated with durvalumab + tremelimumab. However, if an investigator learns of any SAEs, including death, at any time after the subject has been permanently withdrawn from study, and he/she considers there is a reasonable possibility that the event is related to study treatment, the investigator should notify the study The University of Texas MD Anderson Cancer Center and AstraZeneca/MedImmune Drug Safety.

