11.5 Interim Analysis: Safety Monitoring

Any patient who received the first dose of study medication will be included in the ongoing safety monitoring. For trial monitoring and decisions about future trials, a patient will be determined to have an extreme toxicity (ETOX) if either condition is met:

- The patient experiences any grade 3 or higher adverse event (AE) that is possibly, probably, or definitely related to therapy received on this protocol and occurs up to 90 days after the last dose of therapy (durvalumab + tremelimumab). As an exception, any such AE that is potentially treatable with steroids will only count as an ETOX if it does not improve to grade 1 or better within 2 weeks.
- The patient has a delay in surgery of 6 weeks or more due to AE, even if that AE does not meet the definition of ETOX.

Based on the method of Thall (1995)⁹, we will monitor ETOX **continually after the 5th patient** receives treatment. Continuous monitoring will occur monthly. We assume $\Theta_T \sim \text{beta}(0.20, 0.8)$ for the current study, where Θ_T is the probability of a patient experiencing an ETOX. Our stopping rule is given by the following probability statement: $P_T(\Theta_T > 0.20 \mid \text{data}) > 0.90$. That is, we will stop the trial if, at any time during the study, we determine that there is more than a 90% chance that the ETOX rate is more than 20%.

The stopping boundaries for this toxicity rule are to terminate the trial if the number of patients with ETOX compared to the number of patients on trial exceed the limits in table 1, with

operating characteristics for this rule in table 2. After 5 patients, this table will be consulted prior to enrolling each patient. Enrollment will not require waiting for complete information for the previous patient, unless an ETOX in that patient would result in hitting the stopping rule. Boundaries and operating characteristics were calculated in Multic Lean v2.1.

Table 1. Stopping Criteria for Excessive Toxicities Based on ETOX

If there are this many patients with ETOX	3	4	5	6 or more
Stop if this many patients (or fewer) have been evaluated at least once for toxicity	6	10	13	15*

* The trial will stop at 15 patients, but if 6 or more patients experience ETOX, this regimen will be too toxic for further study in this population.

Table 2. Operating Characteristics for Toxicity Monitoring

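### Section 10.1.1 bars collection of AEs attributed to chemotherapy or surgery; this contradicts Section 10.3.1 and can drop events that the ETOX definition counts

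*Combined protocol and SAP*

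**What the plan says.** Section 10.1.1 contains two restrictions. One concerns collection: "AEs attributable to the preplanned neoadjuvant chemotherapy or surgery will not be collected". The other concerns follow-up: "Only AEs related to study drug (durvalumab + tremelimumab) will be followed". The same section defines AE to cover serious and non-serious events.

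Section 10.3.1 has no such limits. AEs and SAEs are recorded from the first protocol intervention, "including the follow-up period (90 +/-7 days after the last dose of durvalumab + tremelimumab", and "all AEs and SAEs should be proactively followed up for each subject". Section 10.1.2 adds that "all SAEs, expected or unexpected, must be reported to the IND Office, regardless of attribution", although that sentence opens with a carve-out for anything the protocol states otherwise.

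ETOX is defined in the synopsis, Section 3.3 and Section 11.5. Its first condition is "any grade 3 or higher adverse event (AE) that is possibly, probably, or definitely related to therapy received on this protocol", up to 90 days after the last dose, with an exception for steroid-treatable events that improve within 2 weeks. In the synopsis and Section 11.5 the second condition is: "The patient has a delay in surgery of 6 weeks or more due to AE". In Section 3.3 it is instead a delay of the same length in starting neoadjuvant systemic therapy.

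Sections 3.2 and 5.2.2 place the start of neoadjuvant treatment within 28 days of the last infusion. The AE record in Section 10.3 has one causality field, yes or no, for the study drugs.

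**The concern.** Sections 10.1.1 and 10.3.1 cannot both be followed. Staff who apply Section 10.1.1 literally and staff who apply Section 10.3.1 literally would record different events for the same patient.

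The difference falls where ETOX is sensitive to it. Most of the 90-day window comes after chemotherapy should have begun. A grade 3 event in that period can plausibly be attributed to chemotherapy and still be possibly related to study drug. ETOX counts it; Section 10.1.1 can be read as keeping it out of the database. An event never entered cannot later be reviewed as possibly related, and the monthly summary to the medical monitor can show only what was entered.

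ETOX feeds the safety part of the primary endpoint, the stopping rule in Table 1, the 95% credible interval, and the conclusion in Section 11.6 that 6 or more ETOX patients make the combination too toxic. Missed events push all of these towards apparent safety.

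**Working it through.** **1. The plan's own figures.** With the beta(0.20, 0.80) prior, stopping requires P(rate > 0.20 | s events in n patients) > 0.90, the posterior being beta(0.20 + s, 0.80 + n − s). It is 0.9275 at 3 of 6, 0.9044 at 4 of 10, 0.9203 at 5 of 13 and 0.9513 at 6 of 15. One more patient at the same count gives 0.8861 (3 of 7), 0.8692 (4 of 11) and 0.8935 (5 of 14). Table 1 is therefore reproduced. An exact binomial recursion with looks from patient 5 to 14 gives early-stopping probabilities of 0.0028, 0.0239, 0.1743, 0.4492 and 0.7244 at true rates of 0.05 to 0.40, against 0.003, 0.02, 0.17, 0.45 and 0.72 in Table 2. The design figures are correct, but they assume that every ETOX is ascertained.

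**2. The exposed part of the window.** Latest on-schedule chemotherapy start: day 28 after the last dose. Days after it: 90 − 28 = 62, or 62/90 = 69% of the post-dose window. An earlier start leaves more.

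**3. Which events are at risk.**

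| Event | ETOX definition | Section 10.1.1 | Section 10.3.1 |
|---|---|---|---|
| Non-serious grade 3+ AE, attributable to chemotherapy and possibly related to study drug | Counts, subject to the steroid exception | No precedence stated; may be left out | Recorded |
| Chemotherapy-attributed AE that delays surgery 6 weeks or more | Counts in synopsis and Section 11.5, where no relatedness is required | Not collected | Recorded if within 90 +/-7 days |
| AE that delays the start of neoadjuvant therapy 6 weeks or more | Counts in Section 3.3 | Arises before chemotherapy, so the chemotherapy exclusion does not reach it | Recorded |

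**4. Illustration of size.** The missed share m is assumed; the documents give no value. Further assumptions: two doses 28 days apart, so the window from first dose is 28 + 90 = 118 days; uniform onset; one qualifying event per ETOX patient; chemotherapy from day 28; all 15 patients treated, with no early stop. The share of the window after chemotherapy start is 62/118 = 0.525. The counted rate is q = p(1 − 0.525m), and the result is P(X ≥ 6) with X ~ Bin(15, q).

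| m | q at p = 0.40 | P(X ≥ 6) | q at p = 0.30 | P(X ≥ 6) |
|---|---|---|---|---|
| 0 | 0.400 | 0.597 | 0.300 | 0.278 |
| 10% | 0.379 | 0.530 | 0.284 | 0.233 |
| 25% | 0.347 | 0.427 | 0.261 | 0.173 |
| 50% | 0.295 | 0.264 | 0.221 | 0.092 |

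If chemotherapy started only at day 70 (28 days plus a 6-week delay), the share is 20/118 = 0.169 and the values at p = 0.40 are 0.576, 0.543 and 0.488.

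**5. Early stopping.** I give no figure for this. Section 11.5 says "Enrollment will not require waiting for complete information for the previous patient", but excepts the case where an ETOX in that patient would reach the boundary. A calculation that ignores this pause would not describe the rule as written.

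**The case against.** The best defence is that Section 10.1.1 and the ETOX definition can be read together: an AE rated possibly related to study drug is a study-drug-related AE and is kept, so only events attributed to chemotherapy alone are lost. Several safeguards help. Sections 6.3.1 and 10.1.4 and Appendix 1 default to an immune cause when there is no clear alternative. Section 10.1.3 lists AEs of special interest, including ALT/AST rises. Section 10.1.2 requires SAE reporting. The steroid exception also means that some lost events would not have counted.

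This narrows the risk without removing it. Section 10.1.1 does not say which attribution prevails. The immune default applies only without an alternative etiology; Appendix 1 names concomitant medications as one, and chemotherapy can be read that way. SAE rules do not reach non-serious events, and Section 10.2.1 confirms that a grade 3 event need not be serious.

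Four stronger readings are tempting but not supported:

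- A reader might infer that at least 62 days overlap chemotherapy. Course length is not stated, and Section 8.1.3 allows surgery directly after the two doses. The 62 days are time after an on-schedule start.
- A reader might infer that Section 10.1.2 contradicts Section 10.1.1 outright. Its opening carve-out lets Section 10.1.1 be read as the exception, and it covers SAEs only. Section 10.3.1 is the clear contradiction.
- A reader might infer that sites would diverge. There is one center; the risk is inconsistent reading by its staff.
- A reader might infer that surgery delays go unseen. Section 11.6 reports them; it is the causing AE that may be absent.

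It also stands that the missed shares have no source, and that a patient with a second, collected event would still count.

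**Conclusion.** The concern holds in this form: Sections 10.1.1 and 10.3.1 conflict on both recording and follow-up, and applying Section 10.1.1 literally can leave out events that ETOX counts. These are non-serious grade 3 or higher AEs with two possible causes and, under the synopsis and Section 11.5, the AE behind a surgery delay. The second part does not arise under Section 3.3, and the differing versions of that condition must themselves be reconciled.

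The conflict is certain from the text; its effect is not. The documents give neither the share of events that would be missed nor the timing of onset, so the drop from 0.60 to between 0.53 and 0.26 at a true rate of 40% is only an illustration under the stated assumptions. It shows that an under-count could matter, not that one will occur. Tables 1 and 2 are not in error. This should be fixed, because an event left out at data entry may be impossible to recover later.

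**What to change.** - Replace the non-collection sentence in Section 10.1.1. Through 90 days after the last dose, collect any grade 3 or higher AE that is at least possibly related to durvalumab/tremelimumab, even when chemotherapy or surgery is another possible cause. Rate relatedness to study drug separately from relatedness to chemotherapy.
- Collect any AE that causes the delay named in the second ETOX condition, whatever its cause. First reconcile the synopsis and Section 11.5 with Section 3.3 on which delay is meant.
- Give Sections 10.1.1 and 10.3.1 the same scope for recording and follow-up.
- State that Section 10.1.1 is not an exception to the SAE rule in Section 10.1.2.

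The cost is a few sentences and a little more data entry for about 15 patients, with no new procedure. An investigator who sees no possible link to study drug can still leave an event out, so the change removes the conflict but not the judgement.

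The downside is over-counting: some chemotherapy toxicity may be rated possibly related. As an illustration at a true rate of 20%, if this happened in 5% or 10% of otherwise ETOX-free patients, the counted rate would be 1 − 0.8 × 0.95 = 0.24 or 1 − 0.8 × 0.90 = 0.28, and the chance of 6 or more of 15 would rise from 0.06 to 0.13 or 0.22. Separate causality ratings limit this risk but do not remove it.
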